#Assessment via telephone or in person

@ Pregnancy test to be performed no greater than 14 days prior to consent in study.

If patients are unable return to the clinic for any of the scheduled assessment days (Day 15, Day 29, Day 36, and/or Day 57), we will contact the patient via telephone to complete the symptom and quality of life assessments (ESAS, HADS, FACT-G, FACIT-F, and GSE). If contacted by phone, then physical assessments will not be performed.

Adverse events will be captured according to the recommended AE recording guidelines for a Phase II protocol.

C.7. Symptom Assessment

C.7.1. Demographic variables

Demographic variables will include patient self-reported birth date, sex, marital status, ethnicity, education, and job status, primary cancer, cancer treatment within the last year, surgery, chemotherapy, immunotherapy or radiotherapy, and medications including opioid dosage. **(APPENDIX P).** Appendix P also includes tracking the baseline labs ordered and an off study note that will be completed once the patient has been taken off study.

C.7.2.Symptom assessment (see Table 3)

The Functional Assessment of Chronic Illness Therapy-Fatigue (FACIT-F) (including the Functional Assessment of Chronic Illness-General (FACT-G) and Fatigue subscales), Hospital Anxiety and Depression Inventory (HADS), Edmonton Symptom Assessment System (ESAS), Symptom Digit Modalities Test (SDMT) and Six minute walk test, will be used assess outcomes.

Adherence: Patients with similar characteristics to those of patients we will admit to the study have demonstrated strong adherence to assessments of the same duration in studies conducted by our group [128,129,137,138]. These assessment tools have been validated and are reliable for use in the collection and analysis of data. Also patients in this study with not undertake time intensive radiological tests such as MRI'S or drug pharmacokinetic studies which are a common part of clinical trials. This would enable help in completion and minimize attrition.

C.7.2.1. Outcome Measures

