This is a preliminary study to explore the efficacy of P. ginseng in reducing fatigue as measured by the Functional Assessment of Cancer Therapy- Fatigue (FACIT-F) subscale. Because this Panax ginseng has not been previously evaluated in cancer related fatigue, we will implement this study in two phases. In the first phase(initial non dose escalating phase), we will enroll up to 30 patients in the Arm 2 (treatment arm); patients will not be enrolled in the placebo arm. Recruitment will be halted until these original 30 patients can be evaluated for DLTs. In the second, main phase patients will be randomized to receive either Panax ginseng or placebo. As a

2009-0854 January 21, 2016 Page 23 of 33

primary analysis, we will assess the level of fatigue at baseline and after 29 days to determine group differences in fatigue changes over time using analysis of variance. This analysis will test for differences between groups, differences over time, and a group by time interaction. We will also perform a repeated measures analysis by group using all available time points (for the FACIT-F fatigue subscale at baseline, day 15 and day 29). This analysis will test for differences between groups, differences over time, a group by time interaction, and trends over time. For all analyses of continuous variables, if the data are not approximately normally distributed, we will either use a nonparametric equivalent of the statistical test or we will transform the variable to achieve approximate normality. The design of the study is intent to treat, i.e., it is our aim to analyze anyone who received at least a single dose for both toxicity and response. Response would be considered clinical beneficial if they improve 3.5 points on the FACIT- F fatigue subscale at day 29 or day 15 (if day 29 is unavailable). Patient who have not completed at least day 15 would be considered inevaluable for consideration of clinical benefit.

Pilot Analysis:

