Evaluable patients will be defined as any patient enrolled on the study that has taken at least one dose of treatment (i.e., either ginseng or placebo), making them available for toxicity and response. Although we expect dropouts (20% of 128 patients) the primary analysis will not include dropouts, but a secondary analysis would carry forward the last known FACIT-F score for those patients who had received at least one dose.

Yearly interim analyses will be conducted by the biostatistician and the results will be presented to the MDACC DSMB office. Results will be presented overall and by arm retaining the blinding as to arm assignment unless requested to reveal arm assignment by the DSMB (usually only made if one or both of the arms show a significantly less than expected efficacy or toxicity). In that case the statistician will reveal the arm assignments to the DSMB. The PI and other collaborators (other than the statistical collaborator) will remain blinded as to the arm assignments of patients.

As a part of each interim analysis, we will determine if either arm has significantly more occurrences of greater than grade 2 adverse events (p<0.05) as compared to each other. If this is found it will be reported to the DSMB and the study may be terminated early.

A formal interim analysis will be conducted when a total of 50 evaluable patients (one-half of the total number of evaluable patients) have been evaluated for 29 days. This interim analysis will allow for the early termination of the study in light of evidence that patients in either arm improve significantly than the other arm (early stopping due to superiority) or that patients in the two arms have similar improvement (early stopping due to futility). In order to provide for an overall two-sided significance level of approximately 0.05 for the study, the interim analysis will have a Lan-DeMets monitoring boundary with an O'Brien-Fleming stopping rule for both tests (EaSt, version 5, Cytel Software Corporation). The decision boundaries for the interim test will be to accept the null hypothesis of no treatment difference (futility) if the test statistic |Z| < 0.348 (p > 0.73), reject the null hypothesis if |Z| > 2.96 (p < 0.003), or otherwise continue the trial. The final test cut-off will be to reject the null hypothesis if |Z| > 1.95 (p < 0.051).

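### The planned check on dropout carries the last FACIT-F score forward, which scores a patient who leaves before Day 15 as exactly zero change and can bias the Day-29 contrast in either direction

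*Combined protocol and SAP*

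**What the plan says.** Section C.9 describes the design as intent to treat and states that "it is our aim to analyze anyone who received at least a single dose for both toxicity and response". Under Power Considerations, after defining evaluable patients by receipt of one dose, the same section says that "the primary analysis will not include dropouts" and that "a secondary analysis would carry forward the last known FACIT-F score for those patients who had received at least one dose".

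The blinded-phase scores are those listed in C.9 and Table 3: "for the FACIT-F fatigue subscale at baseline, day 15 and day 29". There is no FACIT-F assessment between baseline and Day 15.

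Two other planned FACIT-F analyses bear on patients with incomplete data, both in C.9:
- "We will also perform a repeated measures analysis by group using all available time points". The type of model and the treatment of incomplete patients are not stated.
- The clinical-benefit comparison uses a 3.5-point improvement, taking Day 15 when Day 29 is missing. For those who leave sooner, "Patient who have not completed at least day 15 would be considered inevaluable for consideration of clinical benefit".

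For missed visits, the text after Table 3 provides that "we will contact the patient via telephone to complete the symptom and quality of life assessments", and FACIT-F is among these. No dropout split by arm or time is given, and no missing-data sensitivity analysis other than carry-forward is named.

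**The concern.** Carry-forward fills the Day-29 value with one of two fixed guesses and then treats it as observed. A patient who leaves before Day 15 has only a baseline score, so the change is set to 0. A patient who leaves after Day 15 keeps the Day-15 change. If patients who stay change on average, neither guess is centred on what Day 29 would have been, and each arm's mean is pulled toward zero in proportion to its own dropout. This needs no link between dropout and outcome.

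The protocol gives reasons to expect dropout that is not trivial and may differ by arm. Section B.5 limits treatment to four weeks because longer follow-up would lose patients to clinical complications, death or loss to follow-up. The dose-modification table takes patients off study drug for related toxicity.

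At stake is the plan's own check on its 20% dropout. If the completers-only primary result and this analysis disagree, the reader could not tell whether the dropouts or the fill-in rule caused it. If they agree, the agreement is weak reassurance.

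**Working it through.** **Inputs from C.9, Power Considerations:** SD of change 5.8; 50 evaluable and 64 recruited per arm; 20% dropout; two-sided 0.05; 80% power; detectable difference 3.3 (5 at SD 8.8).

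**The plan's own figures reproduce.** Detectable difference = (1.96 + 0.842) x 5.8 x sqrt(2/50) = 3.25 by the normal approximation and 3.28 by the t-test, against 3.3 stated. At SD 8.8 the values are 4.93 and 4.98, against 5. Recruitment: 50/0.8 = 62.5, so 63, against 64 stated.

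**Assumptions (not in the documents):** dropout unrelated to outcome within arm; half of dropouts leave before Day 15; mean Day-15 change is half the Day-29 change; SD 5.8 at both visits; background change m in both arms of -2, 0, 2, 5 or 8 points.

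**Arm mean under carry-forward.** With dropout d and true mean Day-29 change μ:

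(1 - d)μ + (d/2)(0) + (d/2)(μ/2) = μ(1 - 0.75d)

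If all dropouts leave before Day 15 it is μ(1 - d).

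**Equal dropout, d = 0.20.** The difference is 3.3 x 0.85 = 2.8, or 3.3 x 0.80 = 2.64 if all leave early. In the half-early case, power with 64 per arm is about 80%, 76% and 70% at m = 2, 5 and 8. A likelihood-based estimate from the observed scores has about 82%.

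**Unequal dropout, assumed 30% against 10%.** The multipliers are 1 - 0.75 x 0.30 = 0.775 and 1 - 0.75 x 0.10 = 0.925.

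- No effect, 30% on ginseng: 0.775m - 0.925m = -0.15m.
- True 3.3, 30% on ginseng: 0.775(m + 3.3) - 0.925m = 2.56 - 0.15m.
- True 3.3, 30% on placebo: 0.925(m + 3.3) - 0.775m = 3.05 + 0.15m.

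| Background change m | No effect, 30% ginseng / 10% placebo | Type I error | True 3.3, 30% ginseng / 10% placebo | True 3.3, 10% ginseng / 30% placebo |
|---|---|---|---|---|
| -2 | +0.30 | 6% | 2.86 | 2.75 |
| 0 | 0 | 5% | 2.56 | 3.05 |
| 2 | -0.30 | 6% | 2.26 | 3.35 |
| 5 | -0.75 | 12% | 1.81 | 3.80 |
| 8 | -1.20 | 20% | 1.36 | 4.25 |

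Type I error at m = 5 as an example. Variance = (1 - d)(5.8² + m²) + (d/2)(5.8² + m²/4) - mean², which gives 32.02 on ginseng and 33.38 on placebo. SE = sqrt((32.02 + 33.38)/64) = 1.011, and 0.75/1.011 = 0.742. Then Φ(-1.96 + 0.742) + Φ(-1.96 - 0.742) = 0.112 + 0.003 = 0.115. Simulation with 4,000 trials per scenario agrees with these results to within simulation error. In the same simulations the likelihood estimate stays near 5% type I error.

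**If all dropout is before Day 15,** with no effect and 30% against 10%, the bias is 0.20m in size: 0.40, 0.70 and 1.00 points at m = 2, 3.5 and 5, with type I error 7.2%, 11.4% and 17.5%.

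**The case against.** Several points on the other side stand.

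- A reader might infer that carry-forward is the only FACIT-F analysis that keeps dropouts. The documents do not support that. The clinical-benefit comparison keeps patients who reach Day 15, and the repeated measures analysis may keep them too, depending on a model that is not stated. Only for patients who leave before Day 15 is carry-forward the one analysis that clearly assigns a Day-29 change.
- A reader might infer that carry-forward always shrinks a real effect and so is conservative, or that the error depends only on which arm loses more patients. Neither holds. The mean change matters as well: with no effect and no background change there is no bias, with worsening the sign reverses, and with more dropout on placebo and improvement in both arms the benefit is inflated.
- The large figures need unequal dropout and sizeable background change. The 30/10 split is assumed, and 8 points exceeds the 3 to 5 that C.9 calls clinically important. At equal 20% dropout and 2 points of improvement the power loss is about 2 percentage points.
- The calculation makes dropout unrelated to outcome. Under that condition the completers-only analysis is also unbiased, and nothing here shows that a mixed model is right if patients leave because of unobserved worsening.
- The analysis is secondary, in a trial described as preliminary. Four-week treatment and telephone FACIT-F limit missing data, although telephone contact does not help once a patient has withdrawn.

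The fourth point also counts against the plan: in the benign case, carry-forward can add a bias that the analysis it is meant to check does not have.

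**Conclusion.** The concern holds in a limited form. The stated check on dropout sets early leavers to exactly zero change and can bias the Day-29 contrast even when dropout is unrelated to outcome within arm. With equal dropout at the planned 20%, a true 3.3 becomes about 2.8, or 2.64 if all dropout is before Day 15. With an assumed 30/10 split the bias can go either way: +0.3 to -1.2 points under no effect, and about 2.8 to 4.2 for a true 3.3 when placebo loses more.

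These sizes rest on assumed dropout timing, arm split, Day-15 course and background change; the documents give none of these. A reader might infer that the primary result is affected. It is not: that result comes from the completers-only analysis, whose own exclusion of dropouts is a separate matter. Correcting that exclusion by carry-forward would, however, move this bias into the primary result. This should be changed, but the trial's main conclusion does not hang on it.

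**What to change.** In C.9, Power Considerations, replace the carry-forward sentence. State that the dropout analysis is the repeated measures analysis already planned at the start of C.9, fitted as a likelihood-based mixed model to all observed baseline, Day-15 and Day-29 FACIT-F fatigue scores of every dosed randomised patient. Terms: arm, visit and arm by visit, with unstructured covariance. Report the Day-29 contrast between arms with its confidence interval.

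That model assumes data are missing at random, and patients with no post-baseline score add little to it. So add one delta-adjusted multiple-imputation sensitivity analysis, with the range of deltas fixed before unblinding, and report dropout by arm and by time (before Day 15, Day 15 to Day 29).

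Cost: revised wording and some extra programming. No new visits, data or patients are needed. The downside is reliance on the missing-at-random assumption, which the sensitivity analysis is there to probe.

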During the second phase of the study, the DSMB will meet to assess toxicity in an unblinded fashion at defined intervals (annual review) and will terminate the study if the incidence of DLT on either arm is judged by the DSMB to be excessive.

Power Considerations: There are no randomized controlled trials on P.ginseng for the management of CRF. The only intervention with Level I evidence for effectiveness in CRF is exercise. Among the most important clinical trials conducted on the intervention are those of Segal etal [154-156]. They have determined the clinically important difference in fatigue as a result of intervention as compared to placebo. Since these two studies used FACIT-F (our primary outcome) we have used these studies for power/sample size calculation. We postulate that if P.ginseng is an effective intervention we will observe a difference in response at Day 29(primary end point) similar and higher to those observed in the Exercise studies. We plan to include 50 evaluable patients per group. If we assume that our dropout rate will be no higher than 20%, we will recruit 64 patients into each group, for a total of 128 patients. As we could find no other published studies about the use of Panax ginseng in cancer patients, we base our sample size estimate on previous research in resistance exercise training [154]. This study found that the difference between groups in changes in the FACIT F subscale at 24 weeks was 4.78, significant at p=0.002, and was powered to detect a difference of 3.5 points based on a similar study in exercise resistance [155] that found standard deviations in difference scores over 12 weeks of 5.8. Studies such as Cella et al, 2002[156], state that differences of 3-5 points or more on the FACIT-F subscale are clinically important differences. If we assume a standard deviation of 5.8 in difference scores, with 50 evaluable patients per group we will be able to detect differences as small as 3.3 or larger with a twosided significance level of 0.05 and 80% power. With standard deviations in difference scores as large as 8.8, we will still be able to detect differences of 5 points or greater.

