For future investigational studies, analyses of the relationships between inflammatory cytokines and fatigue will also be performed using correlation analyses. The cytokines (serum and Induced monocyte) we will explore in future analyses include IL-1 β , IL-6, IL-10 and TNF- α . Information on cytokines and fatigue will be available at baseline, day 15 and day 29. We plan to explore the correlations between cytokines and fatigue within each time point and between time points.

D.10. Future Studies: The exploratory data gathered will be used to design a larger trial that will also allow for longer longitudinal follow-up of patients to determine the onset and duration of response;

determine whether response to ginseng occurs more frequently in patients with certain primary tumors or disease stages; and to determine adherence to assessments using different tools and timing of different evaluations. A larger study will also allow us to better characterize the role of cytokines versus direct central effects. The preliminary data obtained will allow us to design appropriate larger trials from the important information obtained regarding response, adherence to assessments using different tools, and timing of different evaluations. The trends observed for the secondary objectives of this preliminary study will allow us to conduct larger clinical trials and apply for future grant applications. The associations between symptom interventions as assessed using validated symptom assessment tools, objective measures such as Hand grip strength test and actigraphy, and levels of cytokines including monocyte induction, will justify for future fatigue studies.

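### The interim futility rule words a stop as evidence that the arms improve alike, but at about 25 patients per arm the 95% CI never excludes a 3-point difference in both directions

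*Combined protocol and SAP*

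**What the plan says.** The paragraph on the formal interim analysis in section C.9 sets its timing: "A formal interim analysis will be conducted when a total of 50 evaluable patients (one-half of the total number of evaluable patients". It allows a stop for superiority, or on evidence that "patients in the two arms have similar improvement (early stopping due to futility". The rule itself has three regions. The first is to "accept the null hypothesis of no treatment difference (futility) if the test statistic |Z| < 0.348" (p > 0.73). The second is to "reject the null hypothesis if |Z| > 2.96 (p < 0.003". In between, the trial continues to a final test at |Z| > 1.95.

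Power Considerations, in the same section, gives the clinical yardstick: "differences of 3-5 points or more on the FACIT-F subscale are clinically important differences". It plans on an SD of 5.8 for change scores and considers values up to 8.8.

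The plan gives no equivalence margin, no confidence-interval criterion and no conditional-power criterion for the futility stop. It does not say how a trial stopped in this way would be reported.

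**The concern.** A small test statistic at half the planned information shows that the trial is unlikely to end in a significant result. It does not show that the treatments perform alike. That would need an interval narrow enough to exclude differences that matter. The plan goes beyond the usual technical label for the inner region, because it says the stop rests on evidence of similar improvement. Those words are the only interpretation it gives the team.

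Power Considerations states that no randomized controlled trials of P. ginseng for cancer-related fatigue exist. An early finding of no difference could therefore carry weight while the data were still compatible with a difference that the plan counts as clinically important.

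**Working it through.** **Inputs, all from section C.9.** Interim at 50 evaluable patients, taken as 25 per arm (an even split is assumed). Futility if |Z| < 0.348; superiority if |Z| > 2.96; final cut-off 1.95. SD of change scores 5.8, or 8.8 in the less favourable case. Clinically important difference: 3 to 5 points or more.

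**The plan's own figures.**
- Detectable difference with 50 per arm: (1.96 + 0.842) × SD × √(2/50). This gives 3.25 at SD 5.8 and 4.93 at SD 8.8, matching the stated 3.3 and 5.
- |Z| = 0.348 corresponds to p = 0.728, as stated. The Lan-DeMets O'Brien-Fleming bound at half information is 2.963, matching 2.96.
- With 2.96, 1.95 and the futility stop, overall two-sided alpha is 0.0503.
- At a true difference of 3.3 and SD 5.8, power is 80.6% with the futility rule and 81.5% without it.

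The boundaries therefore do what the plan says.

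**Precision at the interim.** SE = SD × √(2/25). The zone edge is 0.348 × SE. The half-width is 1.96 × SE, or 2.011 × SE with t on 48 df.

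| | SD 5.8 | SD 8.8 |
|---|---|---|
| SE | 1.64 | 2.49 |
| Futility zone, observed difference | ±0.57 | ±0.87 |
| 95% half-width, normal / t | 3.2 / 3.3 | 4.9 / 5.0 |
| CI at Z = 0 (normal) | −3.2 to 3.2 | −4.9 to 4.9 |
| CI at Z = +0.348 (normal) | −2.6 to 3.8 | −4.0 to 5.7 |
| CI at Z = −0.348 (normal) | −3.8 to 2.6 | −5.7 to 4.0 |

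At both SDs the half-width exceeds 3, so no interval in the zone can lie within ±3.

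**Which direction remains open.** The upper limit equals +3 at Z = 3/SE − 1.96. At SD 5.8 this is 1.829 − 1.960 = −0.13, or −0.18 with the t interval. Above that value a 3-point ginseng benefit is inside the CI. This covers 69% of futility stops under the null (77% with t). Below it, +3 is excluded and −3 is inside. The largest upper limit anywhere in the zone is 3.8 (3.9 with t), so benefits of about 4 points or more are excluded. At SD 8.8 both +3 and −3 are always inside.

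**How often the rule fires.** P = Φ(0.348 − d/SE) − Φ(−0.348 − d/SE).
- d = 0: 27.2%.
- d = 3, SD 5.8 (d/SE = 1.829): 5.5%.
- d = 3, SD 8.8 (d/SE = 1.205): 13.5%.

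**Sample size needed to exclude +3.** n per arm = 2 × [SD × (Z + 1.96)/3]². At SD 5.8 this is 29 at Z = 0 and 40 at Z = 0.348. At SD 8.8 it is 67 and 92. The interim has 25.

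**The case against.** Several points on the other side have force.

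- Accept, reject and continue are common names for the three regions of a two-sided boundary, and the plan labels the inner region futility. This would answer the complaint about the word accept alone. It does not answer the separate statement that the stop rests on evidence of similar improvement.
- The 3-point yardstick is the lowest value in the plan's range, and the exercise study it cites found 4.78. At SD 5.8 a futility stop does exclude 4.78 and 5. At SD 8.8 it does not exclude 4.78 over the whole zone: the upper limit runs from 4.0 to 5.7.
- An equivalence analysis would often use a 90% interval. At SD 5.8 its half-width is 2.75, so it fits within ±3 for observed differences within ±0.25. That is less than half of the ±0.57 zone. At SD 8.8 it never fits.
- The effect on trial conduct is small: less than one percentage point of power at 3.3 points and SD 5.8. This stands, and it is why the boundary is left alone.

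A reader might also infer a matching fault in the superiority stop: that its estimate needs a stage-wise correction before it is used under D.10, where "The exploratory data gathered will be used to design a larger trial". The plan has one formal efficacy look. After a stop there, the stage-wise median-unbiased estimate and CI equal the ordinary ones: at Z = 2.97 and SD 5.8, both give 4.87 (1.66 to 8.09). D.10 does not say that the FACIT-F estimate will size the next trial. No change is proposed there.

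**Conclusion.** The conclusion attached to the futility stop is unsupported; the stopping boundary is sound. Following the wording as it stands would declare similarity in about 27% of trials with no true effect, and in 5.5% to 13.5% of trials with a true 3-point difference. In every one of these stops the 95% CI would include a 3-point difference in at least one direction.

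Two stronger readings should be avoided. One is that a 3-point ginseng benefit always remains open after a futility stop. At SD 5.8 it does not for Z below about −0.13 (−0.18 with t); the point rests on similarity being a two-sided claim. The other is that a published report would state that the arms do not differ. The plan has no reporting text, so that is only a possible consequence of its wording.

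The figures assume 25 patients per arm, a common SD of 5.8 or 8.8, and an ordinary 95% CI for the difference in change scores.

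**What to change.** In the formal interim paragraph of C.9, remove both the acceptance of no treatment difference and the reference to similar improvement. Replace them with wording such as: *stop for futility (a significant difference is unlikely to be shown)*. Add that, after such a stop, the between-arm FACIT-F difference is reported with its 95% CI and read against the 3 to 5 point range in Power Considerations, with no claim of similarity or of no difference.

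Boundaries, alpha and sample size are unchanged. The cost is a few sentences and a less definite statement after a futility stop.
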